5.3 Randomization and Concealment

The patients will be randomized to one of the two groups: vertical mattress suture (test group) and horizontal mattress suture (control group) on a 1:1 ratio. Randomization will be performed by computer generated random codes. Allocation will be concealed to the surgeon until completion of all surgical steps except for suturing by opaque envelopes.

5.4 Blinding

As it is not possible to blind the therapist and examiner for the suture, an open-label design will be used in this study

6. The Selection, Withdrawal and Management of Subjects

6.1 Inclusion Criteria

Consecutive patients fulfilling the following inclusion criteria will be invited to participate in the study:

- Aged 18 and above
- Subjects want single implant treatment in esthetic area (premolar to premolar) in maxilla
- With sufficient bone width (≥ 6 mm)
- With mesial-distal distance over 8mm
- Evidence of subject ability to achieve good oral hygiene and control periodontitis in the whole of the dentition (FMPS $<20\%$ and FMBS $<20\%$)
- Ability to understand study procedures and to comply with them for the entire length of the study. Ability and willingness to give written informed consent.

6.2 Exclusion Criteria

All candidates meeting any of the following exclusion criteria at baseline will be excluded from study participation:

- Subjects want multiple adjacent implant treatment
- Patients with inadequate bone volume where major bone augmentation would be required at implant location.

- Subjects with untreated periodontitis
- Current smokers
- Subjects with diabetes mellitus.
- Pregnant females
- Participation in another intervention trial
- Inability or unwillingness of individual to give written informed consent.

6.3 Management of Subjects

(1) Study Enrollment Procedures

Consecutive subjects will be screened for eligibility in the Department of Implant Dentistry of Shanghai Ninth People's Hospital, Shanghai Jiao Tong University School of Medicine. Potentially eligible patients will be provided information about the study objectives by one of the investigators and full informed consent will be sought from potentially interested subjects.

(2) Informed Consent Process

The participant must personally sign and date the latest approved version of the informed consent form before any study specific procedures are performed. Documental consent form will be provided to patient, with verbal explanation by one of the investigators. The procedure would be done at the beginning of the study after verification of inclusion and exclusion criteria.

Written and verbal versions of the participant information and Informed consent will be presented to the participants detailing no less than: the exact nature of the study; the implications and constraints of the protocol; the known side effects and any risks involved in taking part. It will be clearly stated that the participant is free to withdraw from the study at any time for any reason without prejudice to future care, and with no obligation to give the reason for withdrawal.

The participant will be allowed as much time as wished to consider the information, and the opportunity to question the investigators to decide whether they will participate in the study. Written Informed Consent will then be obtained by means of participant dated signature and dated signature of the investigator who presented and obtained the informed consent. A copy of the signed informed consent will be given to the participants. The original signed form will be retained at the study site.

7. Study Procedures

7.1 Treatment of Trial Participants

7.1.1 Control of periodontitis (if needed)

Standard periodontal treatment needs to be completed in the dentition before the patient can be

enrolled into the study. The patient needs to show evidence of good oral hygiene (FMPS<20%) and control of bleeding on probing (FMBS<20%).

7.1.2 Surgical procedures

One experienced specialist in Implant Dentistry will perform the implant surgeries for all patients. Surgery will be standardized, and the same procedures/materials will be employed to ensure consistency.

- Local anesthesia will be performed by infiltration at the buccal vestibular sulcus and the palatal side of the alveolar ridge.
- Following anesthesia, a mid-crestal ridge incision will be started and continue with sulcular incisions around both adjacent teeth to the implant bed using blades #.11 or No.12.
- A full-thickness mucoperiosteal flap will be raised and soft tissue remnants will be removed to fully expose the alveolar ridge.
- A standardized dental implant (Nobel Active) will be placed according to the manufacturer's instructions. Cover screws will be used.
- Different suture techniques will be used according to the group allocation to achieve wound closure after opening the envelope.
- The sutures will be removed after 7 days.

7.1.3 Post-surgical instruction

- Post-operative pain and oedema will be controlled with analgesics (Ibuprofen, TSKF, 600mg, 2 times, interval 6-8 hours). Antibiotic regimen will also be performed (amoxicillin, Xinya Co, 2g, 60 minutes before surgery).
- Rinsing with 0.12% chlorhexidine will be prescribed 3 times/day for the first 2 weeks
- Another single clinician, blind with respect to the group assignment, will perform all measurements.

7.2 Handing of study interventions

Allocation will be concealed to the surgeon until completion of all surgical steps except for suturing. Thereafter, vertical mattress sutures (test group) or horizontal mattress sutures (control group) will be performed according to the group allocation to achieve wound closure after opening the envelope.

(1) Control group

In the control group, the participants will receive the following sutures to achieve wound closure:

- One mesial single interrupted suture (1 mm from the mesial teeth, 2-3mm from needle-in points to the incision)
- One distal single interrupted suture (1mm from the distal teeth, 2-3mm from needle-in points to the incision)
- One horizontal mattress suture (5-6mm from needle-in points to the incision, 3-4mm from needle-in to needle-out points)

(2) Test group

In the test group, the participants will receive the following sutures to achieve wound closure:

- One mesial single interrupted suture (1mm from the mesial teeth, 2-3mm from needle-in points to the incision)
- One distal single interrupted suture (1mm from the distal teeth, 2-3mm from needle-in points to the incision)
- One mesial and one distal vertical mattress sutures (5-6mm from needle-in points to the incision which are in keratinized tissues, 2-3mm from needle-out points to the incision, 3-4 mm from mesial and distal sutures)

7.3 Course of Treatment and Visit Points

7.3.1 Screening and Enrollment

Screening evaluations for this study will be performed in the Department of Implant Dentistry of Shanghai Ninth People's Hospital. Clinical and radiographic assessment will be performed for treatment plan. Subjects fulfilling the inclusion and exclusion criteria will be invited to participate in the study and receive an explanation of the study, its objectives, benefits and risks by the investigator in the context of informed consent. The following information will be collected and recorded after the inclusion of the participants.

(a) Demographics

The date of birth, gender and drinking habits will be recorded.

(b) Medical History

Details of medical, including diabetes mellitus, cardiovascular diseases and other systemic diseases will be recorded.

(c) Concomitant Medication

All over-the-counter or prescription medication, vitamins, and/or herbal supplements will be recorded on CRFs.

The LDF measurements at the test and control group will be performed on the day of the surgery before the injection of the local anaesthesia (baseline), 1min following local anaesthesia induction, immediately following completion of the surgical procedure, post-operative hours 1,2,6 and on post- operative days 1, 3, 7, 14, 30.

(5) Suture tension (Flap Tension Meter)

Immediately after suture, the tension exerted on the flap margins with the respective sutures was measured using a highly sensitive electronic tension/pressure device (Flap Tension Meters, Imedico GmbH, Zurich ZH, Switzerland). Tension was read to an accuracy of 0.001N (0.1 g).

7.3.4 Follow-up Visits and evaluation

Follow-up assessment will be performed by the same trained clinician, blind with respect to the group assignment, additional assessments including:

(1) Soft tissue thickness

The thickness of the soft tissue will be performed with calipers 2 mm from incision margin in both buccal and palatal side.

(2) Clinical wound healing assessment

EHI index will be used for clinical wound healing assessment: a) complete flap closure – no fibrin line in the interproximal area; b) complete flap closure – fine fibrin line in the interproximal area; c) complete flap closure – fibrin clot in the interproximal area; d) incomplete flap closure – partial necrosis of the interproximal tissue; e) incomplete flap closure – complete necrosis of the interproximal tissue.

(3) Patient-reported outcomes

Visual analogue scale (0-10) will be used to evaluate the post-operative pain.

Immediate after anesthesia – T1

- LEA measurement
- Soft tissue thickness (after flap elevation)

Immediate after suture – T2

- LEA measurement
- Intra-oral scanning
- Suture tension
- PROMs

1 hour after surgery – T3

- LEA measurement
- Intra-oral scanning

2 hours after surgery – T4

- LEA measurement
- Intra-oral scanning

6 hours after surgery – T5

- LEA measurement
- Intra-oral scanning
- PROMs

24 hours after surgery – T6

- LEA measurement
- Intra-oral scanning
- Clinical wound healing assessment
- PROMs

72 hours after surgery – T7

- LEA measurement

- Intra-oral scanning
- Clinical wound healing assessment
- PROMs

7 days after surgery – T8

- LEA measurement
- Intra-oral scanning
- Suture removal
- Clinical wound healing assessment
- PROMs

14 days after surgery – T9

- LEA measurement
- Intra-oral scanning
- Clinical wound healing assessment

30 days after surgery – T10

- LEA measurement
- Intra-oral scanning
- Clinical wound healing assessment

8. Outcomes and evaluations

8.1 Outcomes

8.1.1 Primary outcomes

- Blood perfusion volume (PU) change during the observation period

8.1.2 Secondary outcomes

- Blood flow velocity change during the observation period
- Hemoglobin count change during the observation period
- Blood oxygen saturation change during the observation period
- Three-dimensional soft-tissue volumetric changes during the observation period
- Changes in clinical wound healing score during the observation period
- PROMs (VAS)

9. Safety Evaluation

9.1 Adverse Events

The collective evidence from numerous clinical trials reveals consistent findings that implant surgery is a safe and the most effective approach for missing tooth replacement. No adverse events

have been reported. Sometimes implant failure happens, but a second implant placement can be performed after healing.

9.2 Follow-up for Adverse Events

Adverse events (AE), if any, will be managed according to current standard of care for the specific condition. The principal investigators will assess and manage the condition to the best of his knowledge and refer to specialist care if appropriate and in the best interest of the participant. AE will be considered resolved once the principal investigators concur that to be the case.

10. Data Quality Assurance

10.1 Quality Control and Assurance

10.1.1 Training and Calibration

All investigators involved in this study will be trained appropriately for the standard operating procedures including the implant surgery and measurements

- The examiner will be trained and calibrated with the LEA measurements and intra-oral scanning before the start of the study.
- The therapist, who will deliver the implant surgery, will be an experienced specialist in implant dentistry fulfilling the Shanghai requirements.
- The investigator who performs interventions for the test/control groups will be trained in a standardized session including the spacing of the mattress sutures and tension of the knotting.

10.1.2 Protocol Deviations

The study will be conducted in accordance with the current approved protocol, ICH GCP, relevant regulations and standard operating procedures. Protocol deviations will be assessed during regular monitoring.

10.1.3 Regular Monitoring

Regular monitoring for assuring protocol compliance, and data quality at the clinical site, including review of source documents and records, consent forms, etc will be performed by an investigator trained in both GCP and the specific procedures. Furthermore, the clinical research coordinator will audit the case report forms for the first few patients to ensure correct filling of forms. The study will also be monitored by the compliance office of the National Clinical Research Center of Oral Diseases and Clinical Research Center of the 9th People Hospital.

10.1.4 Record Keeping

All investigators are required to keep complete clinical records, clinical samples, study data for all the patients included in the study. Radiographs and intraoral scanning images should be archived

in digital format and stored securely both as part of the patient clinical record and as part of the study records. The study coordinator will collect a copy of all digital files. All research-related records will be retained for at least 5 years after study completion.

10.1.5 Patient Scheduling

In order to improve compliance with protocol, all subjects participating in the study will have an alert in their patient record identifying them as participant to this protocol in order to alert administrative staff on the need to follow a stringent timing of follow-up appointments.

10.2 Data Management

(1) Overview of Data Management Methods

- Primary data will be stored and retrieved from the Shanghai Ninth People Hospital. The participants will be identified by a study specific participant number and/or code in the secondary database after retrieving data from primary database for data analysis. CRF will be in written format with identifiers removed and assigned with identifying codes. Codes will be stored safely and separated from data. The name and any other identifying detail will NOT be included in any secondary study data electronic file. All documents will be stored securely and only accessible by trial staff and authorized personnel.
- The investigators will archive source documents for each patient entered in the study, signed and witnessed informed consent forms, patient questionnaires. Furthermore, the investigators will maintain a study patient list that will allow matching Case Reports with source documents, a screening log, the investigator manual, digital radiographs, intraoral scanning images and clinical samples.

(2) Internal Analysis Plan of Data

N/A

(3) The Frequency of Data Security and Monitoring Reports Submitted to the Ethics Committee

Given the low risk profile of the study, data safety and monitoring reports will be submitted to the Ethics committee every 6 months.

11. Statistical Analysis

11.1 Statistical Software and General Requirements

Data analysis will be performed in SPSS software, version 26.0 (IBM Corp., Armonk, NY, USA).

The level of statistical significance will be set at 0.01 for all tests.

11.2 Statistical analysis plan

- (1) Descriptive statistics will be run to describe the demographic, clinical and biological characteristics of the study population. Means with standard deviations (SD) or medians with interquartile range (IQR) will be used to describe continuous variables. Frequencies will be used to describe categorical variables.
- (2) The normality of clinical and biological parameters at baseline and each re-evaluation visit will be tested for normality using the Kolmogorov-Smirnov test. The homogeneity of the clinical and biological parameters at baseline and each re-evaluation visit will be tested using Levene's test.
- (3) The differences over time within groups for data will be analyzed with the non-parametric Wilcoxon's Signed Ranks tests or Paired t-tests according to the data normality and homogeneity.
- (4) The comparison of parameters between the control and the test group at baseline and each re-evaluation visit will be performed with the Mann-Whitney U test or Student t test according to the data normality and homogeneity, respectively.

12. Ethics Requirements and Informed Consent

The Investigators will ensure that this study is conducted in full conformity with the current revision of the Declaration of Helsinki (last amended October 2013). The Investigators will ensure that this study is conducted in full conformity with relevant regulations and with the ICH Guidelines for Good Clinical Practice E6 (R1) July 1996. The protocol, informed consent form and participant information sheet will be submitted to an appropriate Research Ethics Committee (REC) for written approval. A signed consent form will be obtained from each participant. The consent form will describe the purpose of the study, the procedures to be followed, and the risks and benefits of participation. A copy will be given to each participant and this fact will be documented in the participant's record. The trial staff will ensure that the participants' anonymity is maintained.

13. References

Chaudhary Ehtsham Azmat , Martha Council. Wound Closure Techniques. StatPearls [Internet]. Treasure Island (FL): StatPearls Publishing; 2021 Jan. 2021 Jul 27.

Nick Marsidi, Sofieke A M Vermeulen, Tim Horeman, Roel E Genders. Measuring Forces in Suture Techniques for Wound Closure. J Surg Res 2020 Nov;255:135-143. doi: 10.1016

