5.2 Sample Size

Null hypothesis is that no significant difference of blood perfusion volume change (PU) can be found at each time points between two groups. Alternative hypothesis is Significant difference of blood perfusion volume change (PU) can be found at least one time point between two groups.

Because actual difference of primary outcome between two groups may vary. An adaptive design is adopted to adjust planned sample size, type of comparison according to actual statistics calculated from 20 subjects. If the revised sample size is within the planned sample size then the planned sample size is not to be adjusted. If the revised sample size is larger than planned sample size then the revised sample size will be considered. The study population, intervention and primary outcome will stay the same throughout this study.

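### Section 11.2 lets pre-tests choose the test separately at each visit with about 10 patients per arm, so the effect measure for the primary outcome is not fixed in advance

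*Combined protocol and SAP*

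**What the plan says.** Section 11.2(2) states that clinical and biological parameters, at T0 and at every later visit, "will be tested for normality using the Kolmogorov-Smirnov test", and that homogeneity is checked with Levene's test. Item (3) then picks Wilcoxon or paired t for changes within a group. Item (4) says that the between-group comparison "will be performed with the Mann-Whitney U test or Student t test according to the data normality and homogeneity, respectively". No sentence keeps one test per outcome across visits. The plan also does not say how the two pre-test results combine, whether the Kolmogorov-Smirnov test carries the Lilliefors correction, or whether visit values or changes from T0 are tested.

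Section 11.1 adds: "The level of statistical significance will be set at 0.01 for all tests". It does not say whether this covers the pre-tests.

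Section 8.1.1 makes perfusion change over the whole observation period the primary outcome. Section 5.2 frames the hypothesis visit by visit: "Null hypothesis is that no significant difference of blood perfusion volume change (PU) can be found at each time points between two groups". It also allows the type of comparison to be adjusted "according to actual statistics calculated from 20 subjects". Section 7.3.4 defines wound healing as five ordered categories ("EHI index will be used for clinical wound healing assessment") and pain as a 0-10 scale. Section 11.2 names no separate test for either.

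**The concern.** Student t estimates a difference in means and Mann-Whitney a shift in ranks. If a noisy pre-test decides between them at each visit, the primary outcome has no fixed effect measure, and results at neighbouring visits may not be comparable. The reader cannot tell whether a change in the result between two visits reflects healing or a change of test.

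Three further features make the rule unsuitable:

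- Failing Levene's test sends the data to Mann-Whitney, which is not a remedy for unequal variances.
- Levene's test compares variances between groups and has no clear role in choosing a paired test within one group.
- Nothing keeps the five-category EHI out of a t test.

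The trial is open-label (Section 5.4), so fixing the analysis before data are seen by group is worth having.

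**Working it through.** **Inputs from the documents.** 20 patients (Sections 1 and 5.2), 1:1 allocation (Section 5.3), so 10 per arm before any dropout or increase. Alpha is 0.01 (Section 11.1). There are ten measurement times after T0 (Section 7.3.4), nine of them after suturing (T2 to T10).

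**Plan's own figure.** The 20 cannot be reproduced, because no effect size, SD or power is given. For orientation, with an exact two-sided t test at 0.01 and 10 per arm, power is 29% for a 1.0 SD difference, and 80% power needs 1.69 SD.

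**Assumptions.** Two-sided tests. Mann-Whitney is used if normality is rejected in either arm or Levene's test rejects; otherwise Student t. Perfusion is normal, or lognormal with log-SD 0.5 to 0.7. Between-visit correlation is 0.5 and the true difference 1.2 SD (on the log scale for lognormal data). Simulations used 4,000 to 20,000 trials per setting.

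**1. Strength of the normality test, one arm of 10.** The Lilliefors critical value at 0.01 is 0.304.

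- Pre-test at 0.01: rejection is 7% at log-SD 0.5, 13% at 0.7 and about 26% at 1.0.
- Pre-test at 0.05: about 18% at log-SD 0.5 and 46% at 1.0.
- Uncorrected form: at most about 3% in any setting run.

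**2. Chance that both tests are used for one outcome.** If p is the chance of Mann-Whitney at one visit and the k visits were independent, P(both used) = 1 - p^k - (1 - p)^k.

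- Normal data: three pre-tests at 0.01 give p of about 1 - 0.99^3 = 0.030. With k = 9, 1 - 0.970^9 = 0.24. The simulation with correlation 0.5 gives about 25%. At a pre-test level of 0.05, p = 1 - 0.95^3 = 0.143 and 1 - 0.857^9 = 0.75.
- Lognormal, log-SD 0.5: p = 0.159, so 1 - 0.841^9 = 0.79. With correlation 0.5 the simulation gives 75% to 76%. At log-SD 0.7 it gives 93%.
- Uncorrected Kolmogorov-Smirnov, lognormal, no group difference: 22% to 30%.

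**3. Cost of the pre-test itself.**

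- Type I error per visit stays at 0.005 to 0.011 under equal variances.
- Normal data, 1.5 SD shift: always t 68.6%, planned rule 67.7% to 68.4%, always Mann-Whitney 63.7%.
- Lognormal data, 1.2 SD, Lilliefors at 0.01: raw t 28% to 35%, planned rule 35% to 37%, always Mann-Whitney 40% to 41%. The loss against one fixed rank test is about 3 to 6 points.
- With the uncorrected form the planned rule gives 30% to 35%, so the loss against 41% is 6 to 11 points.

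**4. Effect of adjusting for T0** (1.2 SD, 10 per arm, alpha 0.01; r is the correlation with T0). With equal SDs at T0 and later, the standardised difference is 1.2 on visit values, 1.2/sqrt(2(1 - r)) on change, and 1.2/sqrt(1 - r^2) in ANCOVA.

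| | r = 0.5 | r = 0.7 |
|---|---|---|
| Change: standardised difference | 1.2/1.000 = 1.20 | 1.2/0.775 = 1.55 |
| ANCOVA: standardised difference | 1.2/0.866 = 1.39 | 1.2/0.714 = 1.68 |
| Planned rule on visit values, power | 35% to 44% | 35% to 44% |
| Planned rule on change from T0, power | 40% to 44% | 63% to 71% |
| ANCOVA, power (simulated) | about 55% | about 76% |

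The exact t formula for ANCOVA gives 59% and 79%. The simulated values are lower because that formula ignores chance imbalance at T0.

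**The case against.** The strongest reply is that the rule does little harm. Test size is held, power is within 1 point of always-t for normal data, and for skewed data the rule recovers power that a raw t test would lose. All of this stands under equal variances.

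A reader might infer that pre-testing is what costs this trial its power. The documents do not support that. Setting 35% to 44% against 55% to 76% combines removal of the pre-test, a possible change of scale, and adjustment for T0, and most of the gain comes from the last. Since the primary outcome is a change, the rule may already be meant for change from T0, and the gap then narrows to about 5 to 15 points.

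Other stronger readings also fail. The test can switch between visits but need not, because the plan gives no perfusion distribution or SD. That the pre-tests run at 0.01 is one reading of Section 11.1; at 0.05 they detect more. EHI reaching a t test is possible but not stated, and Section 11.2(1) describes categorical variables by frequencies. The size of 10 per arm is the planned one, and Section 5.2 allows it to grow: "If the revised sample size is larger than planned sample size then the revised sample size will be considered".

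Finally, one fixed test per visit still leaves nine or more separate results. Only a repeated-measures model or a named time point would give a single answer.

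**Conclusion.** The concern holds as a lack of pre-specification. Section 11.2 leaves the test, and so the effect measure, open at every visit, and the pre-tests that decide it are too weak at 10 per arm to guide the choice. Both tests would be used for one outcome in about 25% of trials with normal data and 75% to 93% with lognormal data (nine visits, correlation 0.5, Lilliefors at 0.01), and less often with the uncorrected form. It is not a finding of inflated error, nor of a large power loss from pre-testing: that loss is none to about 6 points against one fixed rank test with Lilliefors, and more only if the correction is omitted. The more useful gain lies in T0 adjustment. The distributions, correlations and 1.2 SD effect are assumptions; the absence of a rule fixing the test is plain from the text.

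**What to change.** Delete the pre-test rule in Section 11.2(2) to (4) and name one analysis per outcome for all visits:

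- **Four laser Doppler measures:** ANCOVA with the T0 value as covariate, or one repeated-measures model with T0 as covariate. Fix the scale, raw or log, before the data are seen by group.
- **EHI and VAS:** Mann-Whitney at every visit where they are recorded.
- **Within-group changes, if still tested:** one named paired method per outcome.
- **Checks:** inspect residuals descriptively, and give a rank-based analysis as a sensitivity analysis.

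The cost is SAP wording. T0 perfusion is already collected, and no patients or visits are added. There are two downsides. The model relies on approximately normal residuals at 10 per arm, which the rank-based analysis helps to check. A log scale would turn the effect into a ratio instead of a difference. This is a cheap improvement.

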3.1 Primary Objective

To compare the peri-implant blood perfusion volume responses during healing with horizontal mattress suture and vertical mattress sutures following open-flap implant surgery.

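### Item (3) of section 11.2 tests change over time inside each arm, which cannot show that the sutures differ, while the between-arm tests in item (4) do not name change from baseline or an arm-by-visit term

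*Combined protocol and SAP*

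**What the plan says.** The primary objective (section 3.1) is comparative: "To compare the peri-implant blood perfusion volume responses during healing with horizontal mattress suture and vertical mattress sutures". Section 5.2 states the hypothesis as a between-group difference in PU change at one or more time points, and section 8.1.1 gives PU change as the primary outcome.

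Section 11.2 has two inferential items. Item (3) is within-arm: "The differences over time within groups for data will be analyzed with the non-parametric" signed-rank test of Wilcoxon or the paired t-test, chosen by normality and homogeneity. Item (4) is between-arm: "The comparison of parameters between the control and the test group at baseline and each re-evaluation visit", by Mann-Whitney U or Student t. Item (4) does not say whether the visit value or its change from baseline is compared, and no item names an arm-by-visit term.

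Section 11.1 adds: "The level of statistical significance will be set at 0.01 for all tests". Section 1 plans 20 patients, and section 5.3 allocates "vertical mattress suture (test group) and horizontal mattress suture (control group) on a 1:1 ratio", so about 10 per arm.

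**The concern.** The question is about the sutures. In section 11, the one item that explicitly analyses change over time does so inside each arm. A within-arm p-value reflects anaesthesia, flap elevation and healing, which act in both arms. It carries no information on whether the course differs between arms.

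Nothing in section 11 labels item (3) descriptive. Its output would therefore allow a report to say that perfusion had recovered by a given visit with one suture and not with the other, because one p-value fell below 0.01 and the other did not. A difference in significance is not a significant difference. With about 10 patients per arm the within-arm test has middling power over a broad range of changes, and that is where two arms with the same true course most often disagree by chance.

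Item (4) is the natural place for the comparison, but it does not name the quantity that the hypothesis is about.

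**Working it through.** **The plan's own figure.** The planned 20 cannot be reproduced, because no effect size, SD or power is given. There is also no stated figure for discordant within-arm results. What follows shows a range under assumptions.

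**Inputs from the documents.** Level 0.01 (section 11.1); 20 patients at 1:1, so n = 10 per arm (sections 1 and 5.3); nine post-suture readings, T2 to T10 (section 7.3.4); paired test within each arm (section 11.2).

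**Assumed, not in the documents.** Two-sided tests; the same true course in both arms; normal changes from T0, with d the mean change divided by the SD of the change; exchangeable correlation between visits of 0.3 to 0.7.

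**Step 1: one visit.** The power p of the paired t-test comes from the noncentral t distribution with 9 degrees of freedom and noncentrality d√10. The chance that exactly one of two identical arms is significant is 2p(1 − p).

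| d | p | 2p(1 − p) |
|---|---|---|
| 0 | 0.010 | 2% |
| 0.5 | 0.103 | 18% |
| 0.8 | 0.310 | 43% |
| 1.0 | 0.504 | 50% |
| 1.2 | 0.696 | 42% |
| 1.5 | 0.896 | 19% |
| 2.0 | 0.993 | about 1% |

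For example, at d = 1.0: 2 × 0.504 × 0.496 = 0.50. Discordance is high between about 0.5 and 1.5 SD and low outside that range.

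**Step 2: any of nine visits.** Simulation of 20,000 trials per setting, with identical arms of 10. A fade is linear from the stated value at T2 to 0 at T10.

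| Common course | Trials with at least one discordant visit |
|---|---|
| No change | 12-16% |
| Fade from 0.5 SD | 35-46% |
| Fade from 1.0 SD | 83-90% |
| Fade from 1.5 SD | 92-94% |
| Fade from 2.0 SD | 87-89% |
| Fade from 2.5 SD | 82-84% |
| Fade from 3.0 SD | 76-79% |
| Constant 0.8 SD | 90-98% |
| Constant 2 SD | 7-11% |
| 2.5 or 3 SD at five visits, then 0 | 6-8% |

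As a check on the first row, nine independent visits with no change give 1 − (1 − 0.0198)^9 = 16.5%. Correlation lowers this, as the simulation shows.

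A large change that recovers gradually has to pass through the zone of 0.5 to 1.5 SD, so it gives high figures. One that ends abruptly skips the zone.

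**Step 3: larger N.** With the fade from 1.5 SD, the figure is about 87-89% at 15 per arm and 82-84% at 20 per arm.

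**Step 4: contrast with a between-arm test.** For identical arms, nine independent between-arm tests at 0.01 give at least one false positive in 1 − 0.99^9 = 8.6% of trials, whatever the size of the common change.

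**The case against.** The strongest reply is that item (4) already supplies a direct between-arm test at every visit. Read with the hypothesis in section 5.2 and the outcome in section 8.1.1, it can be taken as the intended test of PU change. That largely stands. A reader might infer that the plan has no between-arm test, or that it will conclude a suture effect from significance in one arm only. The documents support neither: item (4) exists, and no passage says that discordant within-arm results will be read as a treatment effect. What remains is that item (4) leaves change from baseline unstated, and that nothing marks item (3) as descriptive.

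A reader might also infer that discordance will occur in about 9 of 10 trials. That figure needs a common change near 1 to 1.5 SD fading gradually, or one near 0.8 SD throughout. The documents give no effect size, SD or correlation, and other courses give well under 10%.

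Nor is 10 per arm fixed. Section 5.2 allows adjustment of sample size and of "type of comparison according to actual statistics calculated from 20 subjects", and says "If the revised sample size is larger than planned sample size then the revised sample size will be considered". In the one course checked, doubling the arm size lowers the rate only modestly.

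Finally, section 3 aims to monitor healing dynamics, and describing change within arms serves that aim. This is a reason to keep item (3) as description, not to delete it.

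**Conclusion.** The point holds as a mismatch between question and analysis. Item (3) cannot answer the suture question, and item (4), which can, does not specify the change that the hypothesis and primary outcome are about. This does not depend on any simulated percentage.

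The size of the risk is conditional twice over: on item (3) being read as a comparison, and on the assumed common course. With 10 per arm and nine visits it is about 75-95% for a gradual fade from 1.5-3 SD, about 35-45% for a fade from 0.5 SD, and under 10% for a large change that ends abruptly. The presence of item (4) makes this a matter of tightening the plan; it is not evidence that the trial's conclusions would be invalid.

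**What to change.** In section 11.2:

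- **Item (3):** label it descriptive. Report within-arm change from T0 with its confidence interval, for outcomes that have a T0 value.
- **Item (4), outcomes measured at T0** (PU, the other LDF measures, the intra-oral scans): state that the between-arm comparison is of change from T0. Preferably use one repeated-measures model adjusted for the T0 value, with an arm-by-visit term (SPSS MIXED), and state its covariance structure in advance.
- **Item (4), wound-healing score and pain VAS:** compare the arms at each visit. Section 7.3.3 lists no T0 value for either. In section 7.3.4 the score starts at T6 and PROMs at T2, so change from T0 is undefined.
- **Add one sentence:** any claim that the arms differ in course or in time to recovery rests only on the between-arm analysis.

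The cost is SAP wording, slightly more analysis work and fewer p-values to report. No new data are needed, and the named software can fit the model.
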